11. STATISTICAL METHODS

11.1 Sample size

Based on previous studies of hemostatic product [16,17] it was estimated that 66% of patients receiving the hemostatic agent and 34% of those receiving standard care alone achieve hemostasis after 3 min. To show a difference between the two treatment options at a power of 90% with a significance level of 5%, a sample size of 98 patients (49 per arm) are required for this trial.

11.2 Analysis populations

For this study, two populations will be considered:

Safety population defined as all patients who signed the Informed Consent. This population will be used for the safety and tolerability analyses.

Intention-To-Treat (ITT) population defined as all the randomized patients who received the assigned treatment. This population will be used for the efficacy analyses.

11.3 Methods

The analyses will be performed with SAS version 9.4. All the variables will be descriptively analyzed by treatment and visit (mean, median, standard deviation, minimum and maximum for continuous variables, frequency distribution for categorical variables).

All the analyses to be carried out will be detailed in the Statistical Analysis Plan (SAP) which will be finalized in Version 1.0 before the Data Base freezing. Version 2.0 of the SAP will be prepared after the Data Review Meeting (in which the protocol violations will be evaluated) and will include the list of the patients belonging to the defined populations and the randomization list.

11.4 Treatment comparison at study entry

A descriptive analysis for demographic data and baseline characteristics will be carried out in order to verify the treatment balance at study entry.

11.5 Efficacy analyses

Responder definition

A patient is defined as "Responder" if he/she achieves hemostasis after 3 min. Time to haemostasis is defined as the time required to obtain successful haemostasis in a single bleeding site. At 3 min, the inspection will be made and, if haemostasis is not achieved, the treatment is considered failed and the patient will be defined as "Non-Responder". A patient assigned to the experimental arm (Hemopatch) for whom was not possible, for any reason, to proceed with the assigned treatment (i.e. has to be treated with the standard care) will be considered as "Randomization failure" and excluded from the ITT population.

In accordance with the primary objective of the study, the proportion of responder patients measured at treatment end (i.e. visit 3) will be the primary endpoint.

The treatment comparison will be performed by a χ^2 test.

The test will be two-sided and conducted at the standard 0.05 significance level

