	In a recent published case report [14] the authors reported the feasibility in							
	using HEMOPATCH Sealing Hemostat® for the management of a myocardial							
	wound, performing the procedure on cardiopulmonary bypass, which meant							
	the patient had to be heparinized. Despite these major risk factors for							
	bleeding HEMOPATCH Sealing Hemostat® managed to contain bleeding and							
	seal the wound without needing any suture.							

[figure not shown]

	Primary Objectives						
	To explore whether Hemopatch can improve time to hemostasis						
TRIAL OBJECTIVES	Secondary objectives						
THIAL OBJECTIVES	To explore whether Hemopatch can:						
	reduce the post-operative complications						
	shorten the use of drainage tube after hepatic resection						
	Primary						
	Evaluated comparing the achievement of hemostasis within 3 minutes from the						
	application of the patch in two groups:						
	common surgical techniques + Hemopatch						
	2. common surgical techniques						
	Secondary						
ENDPOINTS	Evaluated comparing the following outcomes:						
LINDFORMIS	the total drainage volume						
	the timing of drainage removal						
	the measurement of total volume of transfused blood products						
	the bile leaks						
	any adverse event						
	the length of hospital stay						
	rate of post-operative mortality						
INCLUSION CRITERIA	 Signed and dated Informed Consent obtained prior to the inclusion in the trial Men and women of any ethnic origin aged 18-75 years Women with childbearing potential willing not to start a pregnancy during the course of the study (at least within the time period foreseen for the patch absorption, i.e. 6-8 weeks from the application of Hemopatch) Men having relationships with women with childbearing potential willing not to procure a pregnancy during the course of the study (at least within the time period foreseen for the patch absorption, i.e. 6-8 weeks from the application of Hemopatch) Patients undergoing liver resection for any underlying disease and with resectable mass. The list of the underlying diseases is the following (but might not be limited to): Hepatocellular carcinoma Hilar cholangiocarcinoma Adrenal cancer metastasis Breast cancer metastasis Colorectal cancer metastasis Biliary carcinoma Hemangioma Hepatic adenoma Focal nodular hyperplasia Unilocular hydatid cyst Multilocular hydatid cyst 						

1. Trauma surgery						
2. Active sepsis around the liver						

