3. STUDY OBJECTIVES

3.1 Primary Objectives

To explore whether Hemopatch can improve time to hemostasis.

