4.2 Design of the study

A phase IV, exploratory prospective, comparative, single blind, randomized trial on the addition of Hemopatch compared to standard techniques to achieve bleeding control after hepatic surgical procedures.

Patients will be randomly assigned to common surgical techniques (ARM A) or assigned to Hemopatch in addition to common surgical techniques (ARM B) in a 1:1 ratio. The study endpoint is the time interval to obtain hemostasis.

Details of the randomization procedure will be specified in an ad hoc separate document of the study.

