 volume of transfused blood products, duration of the surgery, type of hepatic resection, the estimated
 intraoperative blood loss and the use of Pringle's maneuver) Concomitant medications recordings
- Adverse event (intraoperative and not-intraoperative) assessment and recording

The patients randomized to Common Surgical Techniques (CST) will be treated conventionally while the patients randomized to experimental technique (CST + Hemopatch) will be treated conventionally with the adjunct of Hemopatch.

For patients included in ARM B Hemopatch is applied upon the verification made by the surgeon of the presence of an appropriate target bleeding (oozing or moderate) site in the hepatic parenchyma. At the time point of application a stopwatch starts simultaneously (time zero). Time to hemostasis is defined as the time required to obtain successful haemostasis in a single bleeding site. This time will be recorded by the operator delegated by the Principal Investigator and according to the surgeon's observation. At 3 minutes the inspection will be made and, if haemostasis is not

achieved, the treatment is considered failed and the Principal Investigator and/or his delegates is allowed to use additional haemostatic measures (including other topical haemostatic agents).

The time to haemostasis will be recorded before in the patient's medical record and then in the eCRF. The bleeding site will be observed for 1 additional minute (after the first 3 minutes) at the end of the haemostatic procedure and at the end of the surgery, in order to confirm the achievement of haemostasis. At the end of surgery at least one perihepatic Jackson-Pratt drain will be left near the site of resection.

Patients allocated to ARM A, will undergo the conventional hemostatic procedures and therefore also these patients will end up with a perihepatic Jackson-Pratt drain, which will be left near the site of resection.

Visit 4 (+1 day after Surgery): Day 2

- Hematology examinations, which includes: glucose, urea nitrogen, creatinine, sodium, potassium, calcium, total
 cholesterol, HDL and LDL, triglyceride, alkaline phosphatase, LDH, complete blood cell counts with differential and
 platelet counts, APTT, PT, INR, fibrinogen, VES, PCR
- · Liver function test examinations, which include: ALT, AST, ALP, bilirubin and total protein, gamma-GT
- Output (in ml) and characteristics of the perihepatic drains (drain pigmentation, i.e. biliary bloody clear)

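### The 3-minute haemostasis clock is defined only for Arm B: Arm A has no stated time zero

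*Protocol*

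**What the plan says.** **Endpoint.** Section 11.5 states that "the proportion of responder patients measured at treatment end (i.e. visit 3) will be the primary endpoint" and compares the arms with a two-sided chi-square test at 5%. A Responder is a patient who qualifies "if he/she achieves hemostasis after 3 min". The scoring rule follows: "At 3 min, the inspection will be made and, if haemostasis is not achieved, the treatment is considered failed". Section 11.1 sizes the trial on 66% against 34% haemostasis at 3 minutes, with 98 patients.

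**Clock.** The synopsis endpoint is "achievement of hemostasis within 3 minutes from the" "application of the patch in two groups". One of those groups has common surgical techniques alone. In section 5.2 (Visit 3) the relevant paragraph opens "For patients included in ARM B Hemopatch is applied upon the verification made by the surgeon", and the stopwatch then starts at application. The later paragraph on Arm A mentions only conventional procedures and the drain.

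**Checks.** Section 5.2 also has the site watched for one further minute and looked at again at the end of surgery, to confirm haemostasis. Section 11.5 does not mention these checks.

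**Other wording.** Section 4.2 says "The study endpoint is the time interval to obtain hemostasis", and 7.2 repeats it. The primary objective in 3.1 is "To explore whether Hemopatch can improve time to hemostasis".

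**The concern.** A 3-minute proportion can be compared between arms only if the three minutes start at a comparable event. Here the start is a patch that half the patients never receive. For Arm A, someone in theatre must choose a start: the first sight of bleeding, the end of compression, the first conventional measure, or something else. Each choice gives a different effective window.

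Section 7.2 blinds only the patient. Under 5.2 a delegated operator records the time according to the observation of the surgeon, who knows the arm. An undefined start is therefore open to differential timing as well as to plain inconsistency.

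The SAP cannot repair this. Section 11.3 requires its Version 1.0 only before the database is frozen, and a clock start that was not recorded in theatre cannot be recovered then.

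**Working it through.** **1. Which endpoint the plan is sized on.** Inputs from 11.1 and 11.5: 66% and 34%, two-sided 5%, power 90%, 1:1. Pooled normal formula:

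n = [1.960·√(2·0.5·0.5) + 1.2816·√(0.66·0.34 + 0.34·0.66)]² / 0.32² = (1.386 + 0.859)² / 0.1024 ≈ 49.2 per arm.

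Rounded up this is 50 per arm (100 in total), within two patients of the stated 98. Exact power of the uncorrected chi-square test at 49 per arm, by full binomial enumeration, is 90.5%. The stated size reproduces for the 3-minute proportion.

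**2. Where a time zero could come from.**

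| Section | Arm B | Arm A |
|---|---|---|
| Synopsis endpoint | patch application | patch application, which does not occur |
| 5.2, Visit 3 | stopwatch at patch application | none stated |
| 7.1.1 | defines the target bleeding site after 30 seconds of compression; not given as a clock start | same |
| 11.5 | inspection at 3 minutes, start not stated | same |

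**3. What an unequal window could do (illustration; the model is an assumption).** Take a constant hazard giving 34% at 3 minutes: h = −ln(0.66)/3 = 0.1385 per minute. The Arm A rate at window t is 1 − exp(−0.1385·t). The rejection rate is the sum, over all pairs (x, y) with chi-square above 3.841, of Bin(x; 49, p_B)·Bin(y; 49, p_A). With no true effect p_B = 34%; with the planned effect p_B = 66%.

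| Arm A window (min) | Arm A rate | Rejection rate, no true effect | Difference from 66% (points) | Power, planned effect |
|---|---|---|---|---|
| 2 | 24.2% | 18.5% | 41.8 | 99.2% |
| 2.5 | 29.3% | 7.7% | 36.7 | 96.6% |
| 3 | 34.0% | 4.8% | 32.0 | 90.5% |
| 3.5 | 38.4% | 7.2% | 27.6 | 80.2% |
| 4 | 42.5% | 13.8% | 23.5 | 66.4% |

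Short Arm A windows produce false findings almost entirely in favour of Hemopatch (18.4 of the 18.5 points at 2 minutes). Long ones produce them almost entirely in favour of control (13.6 of the 13.8 points at 4 minutes).

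**4. If the confirmation checks decided Responder status.** Suppose 66% and 34% are unconfirmed rates and 10% of 3-minute responders re-bleed in both arms. The rates become 0.66·0.90 = 59.4% and 0.34·0.90 = 30.6%, and exact power at 49 per arm falls to 83.6%. The protocol gives no re-bleed rate.

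**5. If a common start precedes the patch.** The Arm B hazard giving 66% at 3 minutes is −ln(0.34)/3 = 0.3596. If the patch goes on d minutes after the common start and the site behaves like control until then, the Arm B rate is 1 − exp(−0.1385·d − 0.3596·(3 − d)). For d = 0.25 this is 64.1% (exact power against 34%: 86.6%). For d = 0.5 it is 62.0% (81.4%). Again, this is only an illustration.

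**The case against.** A reader might infer that the protocol fixes no single primary endpoint. The documents do not support that. Every place that labels an endpoint primary (synopsis endpoints, synopsis statistics, 4.1, 11.5) names achievement of haemostasis or its proportion. The sample size and the chi-square test also fit the proportion. Sections 4.2 and 7.2 say study endpoint, not primary endpoint. Their sentence contradicts 11.5 and should be corrected, but the intended test is not in doubt. An objective phrased as time to haemostasis with a dichotomised endpoint is ordinary.

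A reader might also infer that Arm A has no 3-minute inspection. Section 11.5 is arm-neutral on that: the inspection and the Responder rule apply to any patient. What is missing is the point from which the three minutes run, without which the inspection cannot be placed in time in Arm A.

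The silence on the confirmation checks is weaker still. Section 11.5 supplies a default, status at the 3-minute inspection, and an SAP that is not shown could settle the rest. It is worth one clarifying sentence and is not a separate defect. Likewise, the inspection sentence shows what is meant by 'after 3 min'.

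Finally, the hazard model and the half-minute and one-minute shifts are assumptions with no source in the protocol. That is correct, so the table shows only that modest timing differences matter. It is no estimate, and it does not show bias towards Hemopatch.

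None of this supplies an Arm A time zero.

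**Conclusion.** The point holds in this form: the primary endpoint is identifiable, but its clock is defined for one arm only. As written, the rule cannot guarantee a comparable 3-minute result in a trial where the surgical team knows the allocation. The actual size and direction of any bias cannot be derived from the protocol. Under the assumed constant hazard, half a minute of mismatch takes the 4.8% rejection rate to 7.2% or 7.7%, and a full minute takes it to 13.8% or 18.5%, depending on direction. The stated 98 patients are not in dispute. The contradiction in 4.2 and 7.2, the 'after' and 'within' wording and the role of the confirmation checks are corrections of wording. This should be changed, with medium confidence, because practice in theatre may already use a consistent start that the protocol does not record.

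**What to change.** - **One time zero.** In the synopsis endpoint, 5.2 and 11.5, name the same event for both arms. A candidate already in the protocol is the surgeon's verification of the target bleeding site as defined in 7.1.1, after the 30-second compression; site evaluation is already a Visit 3 step not limited to an arm. Starting Arm A at its first conventional measure and Arm B at the patch would not be comparable, because Arm B also receives conventional techniques. Time from patch application can still be recorded in Arm B as a secondary time.
- **Same measurement.** Require the same stopwatch, 3-minute inspection, confirmation checks and recording in both arms. Section 5.2 also ties the 3-minute inspection to the use of additional measures. The amended text must say which clock that sentence refers to; that is for the investigators to settle.
- **Wording.** Bring the endpoint sentence in 4.2 and 7.2 into line with the responder proportion in 11.5, and replace 'after' by 'within' 3 minutes wherever the rate is defined.
- **Responder rule.** State in 11.5, before outcomes are seen, that the 3-minute inspection decides Responder status, with haemostasis confirmed at the 5.2 checks as a sensitivity analysis. On this definition the checks give no reason to change the 98 patients.

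The cost is a protocol amendment (12.2, 13.1) and timed recording in Arm A. Because a common start would precede the patch, the Arm B rate may fall somewhat, so the 66% assumption, and with it the power at 98, should be checked against the new clock.

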7.2 Randomization

A phase IV randomized comparative design with specific statistical tests will be carried out. Patients will be randomly assigned to standard (ARM A) or experimental (ARM B; Hemopatch in addition to common surgical techniques) with a 1:1 ratio. The study endpoint is the time interval to obtain hemostasis.

Assigned treatment ARM will remain unknown to the patients, while physicians will use the treatment assigned according to the randomization list.

The randomization will be performed at the visit 2 - baseline, before surgery. Details on the randomization process managing and possible stratification factors to be considered will be included in a specific document, which will be finalized before the study starting.

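### The only efficacy population is called ITT but requires receipt of the assigned treatment and drops unpatched Hemopatch patients, which leaves the primary test open to bias in either direction

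*Protocol*

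**What the plan says.** Section 11.2 of the protocol names two populations, Safety and ITT. The ITT population is "defined as all the randomized patients who received the assigned treatment", and it is the only one assigned to the efficacy analyses.

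Section 11.5 adds a rule for the experimental arm alone. A Hemopatch patient "for whom was not possible, for any reason, to proceed with the assigned treatment (i.e. has to be treated with the standard care") is classed as a randomisation failure "and excluded from the ITT population". The same section makes the proportion of responders the primary endpoint, tested by a two-sided chi-square test at 0.05.

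Three other places determine who can meet that rule:

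- **Timing (section 7.2):** "The randomization will be performed at the visit 2 - baseline, before surgery".
- **Blinding (section 7.2):** only the patient is blinded, "while physicians will use the treatment assigned according to the randomization list".
- **Application (section 5.2, Visit 3):** in Arm B, "Hemopatch is applied upon the verification made by the surgeon of the presence of an appropriate target bleeding (oozing or moderate) site".

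For Arm A, section 5.2 says only that conventional haemostasis is used. The target site is evaluated and recorded at Visit 3 without reference to arm (sections 5.1 note 7, 5.2 and 7.1.1). No section makes a target site a condition for analysing an Arm A patient.

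**The concern.** A population that requires receipt of the assigned treatment is a per-protocol type of set, whatever its label. Here the condition bears unequally on the arms. A resected Arm A patient receives conventional haemostasis almost by definition. A resected Arm B patient must also pass the surgeon's intraoperative judgement that the patch can be used. That judgement concerns the bleeding itself, so it is closely tied to the 3-minute outcome, and it is made with the arm known.

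The primary test may therefore compare a selected Arm B with a less selected Arm A. No all-randomised efficacy analysis is stated that would show this. These rules are written into the protocol, so an analysis plan that follows them inherits the problem.

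**Working it through.** **Inputs.** From section 11.1: 66% v 34% response, 90% power, 5% significance, 49 per arm. From section 11.5: two-sided chi-square test at 0.05. The protocol gives no share of Arm B patients who will not be patched and nothing on how they would respond. Both are assumptions below.

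**The plan's own figure.** With pooled variance under the null (mean rate 0.50):

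n = [1.960·√(2·0.5·0.5) + 1.282·√(0.66·0.34 + 0.34·0.66)]² / 0.32² = (1.386 + 0.859)² / 0.1024 ≈ 49.2 per arm.

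The stated 49 is reproduced within rounding. Exact binomial enumeration of the uncorrected chi-square test at 49 v 49 gives power 90.5%. With 34% in both arms, the chance of a significant result is 2.4% in each direction.

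**Effect of the exclusion when the treatment does nothing.** Let the true response be 34% in both arms. A share f of Arm B is dropped, and those dropped would have responded at rate r. All 49 Arm A patients stay. The remaining Arm B patients then show

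p′ = (0.34 − f·r) / (1 − f).

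For f = 10%, r = 0 gives 0.34/0.90 = 37.8% and r = 1 gives 0.24/0.90 = 26.7%. The rejection probability is enumerated exactly, with the number dropped taken as binomial(49, f).

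| Share of Arm B dropped | 5% | 10% | 15% | 20% |
|---|---|---|---|---|
| r = 0 (all would fail): apparent Arm B rate | 35.8% | 37.8% | 40.0% | 42.5% |
| r = 0: false win for Hemopatch | 3.8% | 5.7% | 8.7% | 12.9% |
| r = 17%: false win for Hemopatch | 3.1% | 3.9% | 4.9% | 6.3% |
| r = 34%: false win for Hemopatch | 2.5% | 2.5% | 2.5% | 2.6% |
| r = 1 (all would respond): apparent Arm B rate | 30.5% | 26.7% | 22.4% | 17.5% |
| r = 1: false result against Hemopatch | 5.5% | 11.6% | 22.9% | 41.8% |

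The rows r = 0 and r = 1 are limits. The first fits patients judged to bleed too severely for the patch. The second fits patients whose bleeding was already controlled, with comparable Arm A patients kept and counted as responders.

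**Power once patients are analysed as assigned** (exact enumeration, 66% v 34% among patients treated as planned):

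- If a common target-site rule removes 10% of each arm (49 × 0.9 ≈ 44), power at 44 v 44 is 85.2%.
- If all 49 v 49 are kept, 10% of Arm B are unpatched and these respond like controls, Arm B is 0.9·0.66 + 0.1·0.34 = 62.8% and power is 83.5%.
- If those unpatched patients all fail, Arm B is 0.9·0.66 = 59.4% and power is 73.3%.

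**The case against.** **Section 11.2 applies to both arms.** This is formally right. An Arm A patient given Hemopatch instead of the assigned treatment would drop out, and patients found unsuitable for resection could leave either arm (exclusion criterion 9 in section 6.2; section 6.3). A reader might infer that the text can never remove a resected Arm A patient, and that goes too far. What stands is that Arm A has no counterpart to the section 11.5 rule, and that section 11.2 is unlikely to remove many resected Arm A patients.

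**The target site is assessed in both arms.** Recording it is arm-neutral, and section 11.5 defines the outcome for one site: "Time to haemostasis is defined as the time required to obtain successful haemostasis in a single bleeding site". One could argue that an Arm A patient without a site would be left out too. The text does not say so, and the Arm A rule remains unsettled.

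**Patch failures.** Sections 6.3 and 8.1 mention patients withdrawn or dropped out because Hemopatch failed, so a reader might infer that failures also leave the analysis. They do not: section 11.5 classes a patient without haemostasis at 3 minutes as a non-responder, and the other two passages concern safety follow-up.

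**Oversight and purpose.** The Data Review Meeting (section 11.3) makes exclusions traceable, but cannot undo an exclusion fixed in advance for one arm. The trial is labelled exploratory, yet it has a 90% power calculation and a formal 0.05 test.

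**Size.** No material effect has been shown, and this objection stands in full.

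**Conclusion.** The point holds as a fault in the stated rule. The ITT label does not match its definition, and the Arm B exclusion depends on an unblinded judgement made after randomisation, with no equivalent for Arm A. The primary test is therefore open to bias.

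Neither direction nor size can be read from the protocol. A reader might infer that the rule favours Hemopatch. The documents do not support that: it does so if the dropped patients are the harder bleeders, works against Hemopatch if their bleeding was already controlled, and is harmless if they respond like the rest. On the assumed shares of 5 to 20%, the limiting cases run from 3.8 to 12.9% false wins for Hemopatch and from 5.5 to 41.8% false results against it, compared with 2.4% in each direction without exclusions. The large figures need a high non-application rate and dropped patients who are all of one kind.

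This should be corrected because it concerns the sole population for the primary test and the correction is cheap.

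**What to change.** **Populations.** In section 11.2, define ITT as all randomised patients, analysed as assigned. In section 11.5, delete the randomisation-failure exclusion and run the primary test by assigned arm, whether or not the patch was applied. Keep the present set, renamed per-protocol.

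**Any removal.** If patients without resection or without a target bleeding site are to be left out of the primary test, use one rule, worded identically for both arms and recorded before the arm-specific step. Two matters must be settled first:

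- The site descriptions must be reconciled. Sections 5.1 (note 7) and 5.2 use two severity grades, oozing and moderate. Section 7.1.1 defines the site by bleeding that persists after compression and uses three grades, up to spurting. As written, it is unclear whether severe bleeders have a target site.
- One time zero must exist in both arms. Section 5.2 ties it to the patch: "At the time point of application a stopwatch starts simultaneously (time zero").

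**Reporting.** Tabulate removed patients by arm with reasons. The surgeon still knows the arm when recording the site, so a common rule reduces selection without excluding it.

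**Sensitivity analyses.** On all randomised patients, impute those removed in all four combinations: responder or non-responder in each arm. The crossed cases are needed, because treating both arms alike does not give the extremes.

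**Cost.** Wording, a few tables and a less favourable stated power. The as-assigned figures under working range from 73.3% to 85.2% when 10% are affected, against 90.5% at 49 v 49. The sponsor should state an expected non-application share and decide whether 98 patients still suffice.
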